3.2. PET/MRI

Since its introduction, positron emission tomography (PET) / computed tomography (CT) has revolutionized oncologic imaging [8]. Utilizing the tracer 2-deoxy-2-[¹⁸F]fluoro-D-glucose (FDG), a glucose analogue, PET/CT readily identifies hypermetabolic lesions and localizes them to specific anatomic locations. Consequently, FDG-PET/CT has become the standard of care for the initial staging and subsequent treatment response assessment for numerous solid neoplasms throughout the body, including the chest and abdomen [9,10]. However, due to certain intrinsic limitations of CT, PET/CT is often supplemented by magnetic resonance imaging (MRI), which provides excellent soft tissue contrast, in order to assess local tumor extent. Moreover, some tumor types are not significantly hypermetabolic relative to their surrounding normal tissues in which they arise, thereby reducing the utility of PET imaging with FDG. Hybrid PET/MRI scanners, which acquire PET data and MRI data simultaneously, have the potential to streamline oncologic imaging protocols by providing the functional and anatomic information necessary for accurate whole-body tumor staging in a single examination.

PET/MRI offers potential advantages over PET/CT or MRI alone for the locoregional staging of rectal cancer (see subsequent section for discussion of metastatic staging). Although highly accurate for determining the extramural depth of tumor spread and detecting involvement of the mesorectal fascia (i.e., T-staging) [11,12], MRI generally relies on size criteria alone for the determination of nodal involvement. For example, one study found that using a short-axis diameter of > 5 mm to define nodes as suspicious results in an overall accuracy of only 34% [13]. In contradistinction, FDG-PET/CT has been shown to have an overall accuracy of 79% for nodal staging (N-staging) [14]. Thus, PET/MRI may have the ability to combine the excellent T-staging accuracy of MRI with the relatively higher N-staging accuracy of PET/CT. This advantage could be particularly valuable to patients with lymph node metastases that would otherwise be outside of the standard surgical/radiation field. Currently, due to limited evidence, PET does not generally play a role in T-staging. However, FDG-PET may provide useful adjunctive information in determining local tumor extent and assessing treatment response [15–17].

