4.2. Secondary objective

To estimate the added value of PET/MRI relative to MRI only for detecting residual or recurrent rectal cancer following chemoradiation in patients on an NOM protocol.

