10.2. Secondary objective

The secondary objective is to estimate the added value of PET/MRI relative to MRI only for detecting residual or recurrent rectal cancer following chemoradiation in patients on a NOM protocol. The MRI component of the PET/MRI will be performed as a standard-of-care examination, with the formal study interpretation flowing to the subject’s medical record and replacing the interpretation that would normally be provided by the clinical reading room. These interpretations will include descriptions of local tumor extension (T-stage) and locoregional lymph node involvement (N-stage). Any potential sites of metastatic disease (M-stage) will also be described, though assessment will be limited to the pelvis. For post-treatment imaging studies, an mrTRG will also be provided according to a standardized scale.

Then, the same study reader interpreting the MRI (initially blinded to the PET data) will qualitatively and quantitatively (e.g., post-treatment SUV_{max}) assess the reconstructed PET images (with and without MRI fusion). This reader will then render a PET/MRI tumor regression grade (pmrTRG) based on the PET and MRI data, using a standardized scoring system. Changes in the perceived disease status (i.e., mrTRG vs. pmrTRG; **the secondary endpoint**) will be recorded. This study interpretation will also flow to the patient’s clinical chart via a separate report. The patient’s multidisciplinary care team will consider the pmrTRG in conjunction with results of other available data (e.g., lower endoscopy and DRE) and make a decision whether to categorize the case as cCR.

Subjects deemed to have anything other than cCR will be evaluated for surgical management (TME or endoscopic resection). In contrast, subjects deemed to have a cCR will continue on the NOM surveillance protocol, with repeat PET/MRIs at regular intervals as indicated in the Schema (also see 7). These subsequent PET/MRIs will be analyzed as outlined in the preceding two paragraphs. Thus, the secondary endpoint will consider all scans that each patient undergoes, rather than just the first scan (as outlined in 10.1 for the primary endpoint). Pathology and clinical follow-up

data will be collected for up to 5 years after enrollment of the patient in the study for correlation with the PET/MRI findings.

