11. STATISTICAL CONSIDERATIONS

The primary endpoint is the feasibility of PET/MRI for rectal cancer treatment response assessment and post-treatment surveillance for patients receiving chemoradiation as part of an NOM strategy. We are interested in the feasibility of PET/MRI for this indication to aid in the planning of a larger prospective trial of short-course radiation therapy followed by adjuvant chemotherapy for the NOM of rectal cancer patients, potentially using PET/MRI to assess for residual or recurrent disease following chemoradiation.

The primary endpoint, feasibility, will be analyzed using descriptive statistics, including exact 95% confidence intervals. Similarly, the secondary endpoint, changes in perceived disease status resulting from the addition to FDG-PET to MRI, will also be analyzed with descriptive statistics, including exact 95% confidence intervals.

A sample size of 20 patients, with an anticipated average of 3 scans/patient, will provide approximately 60 scans for feasibility assessment. If we observe a feasibility rate of 83.3% (i.e., 50 of 60 scans completed imaging sessions with adequate image quality), the exact 95% confidence interval for that proportion and sample size would be 72-92%. The lower limit of this confidence interval will effectively indicate that feasibility is $\geq 70\%$ and that the study has met its primary endpoint.

If a feasibility rate of 90% is observed for the first 20 scans after the optimization phase, the 95% confidence interval for that rate would be 68.3-98.8%. This lower bound will be deemed close enough to 70% to constitute success with respect to achieving the primary endpoint. Thus, enrollment of additional subjects could cease at this point (**early stopping**) at the discretion of the Principal Investigator. Notably, already enrolled subjects would continue receiving additional scans per protocol and will be included in the secondary endpoint analysis.

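### The secondary endpoint compares regression grades only, so a nodal or other pelvic call that PET adds or clears has no prespecified place in it

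*Combined protocol and SAP*

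**What the plan says.** Section 4.2 gives the secondary objective: "To estimate the added value of PET/MRI relative to MRI only for detecting residual or recurrent rectal cancer following chemoradiation". Nothing restricts it to the primary tumor site.

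Section 10.2 describes two consecutive reads by one reader. The first uses MRI only, blinded to PET. On its content the section says "These interpretations will include descriptions of local tumor extension (T-stage) and locoregional lymph node involvement (N-stage"), and then "Any potential sites of metastatic disease (M-stage) will also be described, though assessment will be limited to the pelvis". Post-treatment scans also receive an mrTRG. The reader then assesses the PET images qualitatively and quantitatively, with and without fusion. The only categorical call specified at that stage is this: "This reader will then render a PET/MRI tumor regression grade (pmrTRG) based on the PET and MRI data, using a standardized scoring system". The endpoint follows, in words that begin "Changes in the perceived disease status (i.e., mrTRG vs" and are completed by pmrTRG.

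Section 11 uses broader words, "changes in perceived disease status resulting from the addition to FDG-PET to MRI, will also be analyzed with descriptive statistics", with exact 95% confidence intervals. It names no nodal or other pelvic component and sets no target.

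On rationale, section 3.2 says "PET/MRI may have the ability to combine the excellent T-staging accuracy of MRI with the relatively higher N-staging accuracy of PET/CT". It also says PET may help with local extent and response assessment. For the post-chemoradiation setting, it argues that PET and MRI response metrics may complement each other.

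**The concern.** The objective concerns disease detection, while the endpoint measures a change in regression grade. The plan lists the grade alongside T-, N- and M-stage as an additional item, which suggests that it describes the treated tumor and not the nodes. If so, two kinds of scan would be recorded as unchanged although PET altered the disease call: one where MRI reads the nodes as negative and PET makes one suspicious, and one where PET clears a node that MRI called suspicious.

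The study is meant to guide a larger trial that may use PET/MRI to look for residual or recurrent disease. A change rate that leaves out nodal and other pelvic calls could understate what PET contributes, and the report would not show by how much.

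**Working it through.** **1. The two reads side by side (section 10.2, post-treatment scans).**

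| Item | MRI-only read | Read after PET is unblinded | In the endpoint? |
|---|---|---|---|
| Regression grade | mrTRG | pmrTRG | Yes |
| Local extent (T) | Recorded | No matching call specified | No |
| Nodes (N) | Recorded | No matching call specified | No |
| Other pelvic sites (M) | Recorded | No matching call specified | No |

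The grade comparison is introduced as the definition of the endpoint, not as an example. A before/after comparison exists for the first row only. Neither scale is identified, and nothing says that mrTRG and pmrTRG share one. Section 3.2 mentions both a 5-point and a 3-point mrTRG.

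**2. What the plan's accuracy figures can and cannot show (section 3.2).**

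- Nodal accuracy is 34% for an MRI size criterion in one study and 79% for FDG-PET/CT in another: 79 − 34 = 45 points. Both figures come from a discussion of locoregional staging.
- After chemoradiation, a cited 48-patient cohort found MRI correct for N-stage in 68–70% and for T-stage in 47–68%. If the 79% carried over to this setting, which the documents do not say, the nodal gap would be 79 − 70 = 9 to 79 − 68 = 11 points.

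Neither gap is an expected effect in this study.

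**3. The plan's own intervals.** The exact (Clopper-Pearson) limits for x of n are

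- lower = Beta⁻¹(0.025; x, n − x + 1)
- upper = Beta⁻¹(0.975; x + 1, n − x)

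For 50/60 this gives 71.5–91.7% (stated: 72–92%, a rounding difference at the lower limit). For 18/20 it gives 68.3–98.8%, as stated. Both concern the primary endpoint. The plan gives no figure for the secondary endpoint.

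**4. Illustration with assumed counts.** Take n = 60 (section 11: 20 patients × 3 scans). Let t be the scans with a grade change, and k the further scans where only a nodal or other pelvic call changes. The endpoint as written reports t/n; the rate for any change is (t + k)/n; the difference is k/n.

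| t | k | Grade change only | Any change | Difference |
|---|---|---|---|---|
| 3 | 0 | 5.0% (1.0–13.9) | 5.0% (1.0–13.9) | 0 points |
| 3 | 3 | 5.0% (1.0–13.9) | 10.0% (3.8–20.5) | 5 points |
| 3 | 6 | 5.0% (1.0–13.9) | 15.0% (7.1–26.6) | 10 points |
| 6 | 0 | 10.0% (3.8–20.5) | 10.0% (3.8–20.5) | 0 points |
| 6 | 3 | 10.0% (3.8–20.5) | 15.0% (7.1–26.6) | 5 points |
| 6 | 6 | 10.0% (3.8–20.5) | 20.0% (10.8–32.3) | 10 points |

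Two limits apply. First, 60 is the feasibility denominator and can include initial-staging scans, which have no mrTRG. If all 20 patients entered at enrollment point #1, 60 − 20 = 40 scans would be post-treatment, and k = 6 would be 6/40 = 15 points. Second, the intervals treat repeat scans in the same patient as independent.

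**The case against.** The strongest reply is that the endpoint fits the setting. The objective concerns disease after chemoradiation, and the rationale in section 3.2 for that setting is complementary response metrics (regression grade, response index, SUVmax). A comparison of mrTRG with pmrTRG addresses that directly. Section 10.2 also makes pmrTRG the named imaging input to the judgement of complete clinical response. This stands, and it is why the grade comparison should stay.

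A second reply is that nodal information is not lost. Section 7.4 requires a full PET dictation, section 10.2 provides a separate report to the chart, and the wording in section 11 is broad. That is true of the raw information. A dictation is not a prespecified paired call, however, and section 11 does not create one.

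A reader might also infer several stronger points that the documents do not support:

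- *Nodal accuracy is the plan's main reason to expect added value.* It is one expected advantage, given for locoregional staging. After treatment, the cited MRI figures extend lower for T-stage than for N-stage.
- *The endpoint misses a 45-point advantage.* The two figures come from separate studies and are not presented as post-chemoradiation results.
- *Nodes are definitely excluded.* The pmrTRG scale is not described and draws on both PET and MRI data, so nodes might influence it. That should be settled in the text.
- *Shifts between two grades that both mean residual tumor will be miscounted as added value.* The plan says only that changes are recorded, and the scale is not stated.

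**Conclusion.** The point holds as a gap between objective and endpoint. Followed as written, section 10.2 provides no before/after comparison of nodal or other pelvic status, so a PET-driven change there with an unchanged grade has no defined place in the secondary endpoint. This rests on reading the regression grade in its ordinary sense, as a description of the treated tumor.

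The size is unknown. The range of 0 to 10 percentage points for 0 to 6 such scans in 60 is arithmetic on assumed counts; with no such scans nothing changes. The endpoint is descriptive, in a 20-patient pilot, with no target or test, so no design figure is affected and the primary endpoint is untouched.

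This is a cheap improvement. It is not a reason to replace the grade endpoint with a binary any-site endpoint: that would give up the graded response information that section 3.2 argues for, and the choice is debatable.

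**What to change.** In section 10.2:

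- Keep mrTRG versus pmrTRG, name the scale, and state that both grades use it.
- On each post-treatment scan, have the same reader, in the same session after PET is unblinded, record again local residual or regrowth (present/absent), N-status and pelvic M-status. Record local present/absent on the MRI-only form as well, so that every call has a pair.

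In section 11:

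- Beside the grade change, report the proportion of post-treatment scans with a changed disease call at any pelvic site. Split it into local, nodal and other pelvic, and by direction (absent to present, present to absent).

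The cost is a few read-form fields and one more descriptive table. No extra scan, reader or patient is needed. The fields should be in place before reading continues, because a call not recorded during the sequential read cannot be cleanly recreated afterwards.

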7.4. Image storage and interpretation

All MR images will become part of a subject's permanent medical record and receive a full dictation by a qualified radiologist, as per standard-of-care procedures. The PET images will also become part of the subject's permanent medical record (i.e., sent to clinical PACS, EPIC, ClinDesk). A full clinical dictation for the PET will also be generated by an individual with expertise in both MRI and Nuclear Medicine to accompany the images in the medical record. See 10.2 for more details on the image interpretation.

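### After a patient's first protocol PET, the mrTRG is not assured to be an MRI-only comparator, yet 10.2 and 11 pool all scans into one change rate

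*Combined protocol and SAP*

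**What the plan says.** Section 4.2 sets the secondary objective: the value that PET/MRI adds to MRI alone for finding residual or recurrent disease after chemoradiation. Section 10.2 turns this into an endpoint: "Changes in the perceived disease status (i.e., mrTRG vs. pmrTRG").

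The relevant steps are:

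- **Reading order.** Within a session, the PET is assessed by "the same study reader interpreting the MRI (initially blinded to the PET data"), who then assigns the pmrTRG. An mrTRG is given only on post-treatment scans.
- **Status of the MRI read.** It is the formal clinical read, "replacing the interpretation that would normally be provided by the clinical reading room".
- **Where the PET result goes.** Section 10.2: "This study interpretation will also flow to the patient’s clinical chart via a separate report". Section 7.4: "The PET images will also become part of the subject's permanent medical record", together with a full PET dictation.
- **Later sessions.** "These subsequent PET/MRIs will be analyzed as outlined in the preceding two paragraphs". No further blinding step is added.
- **Analysis set.** "the secondary endpoint will consider all scans that each patient undergoes, rather than just the first scan".

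Section 11 plans descriptive statistics with exact 95% confidence intervals for this endpoint. It gives no expected change rate and no split between first and later scans.

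**The concern.** A change from mrTRG to pmrTRG measures what PET contributes only if the mrTRG was formed without PET. The blinding as written covers the PET of the current session. By the next session, the earlier PET images, PET dictation and pmrTRG are in the record, and the MRI read is an ordinary clinical read for which the record is open. No sentence keeps that material from the reader. The mrTRG may then already carry PET information, and the comparison becomes new PET against MRI plus old PET.

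Pooling hides this, because one rate mixes reads made before any protocol PET with reads made after one. There is also an interval problem: an exact binomial interval on scans counts several scans of one patient as independent observations.

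The overview in section 2 says that the data will inform the design of later trials. A change rate whose comparator shifts between sessions is hard to carry forward.

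**Working it through.** **1. The plan's own intervals.** Section 11 gives figures only for the primary endpoint. Clopper-Pearson on 50/60 gives 71.5-91.7% (stated: 72-92%). On 18/20 it gives 68.3-98.8% (as stated). The exact interval is thus the binomial one with the scan as unit. I assume the same method for the secondary endpoint, for which section 11 uses the same wording.

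**2. Share of sessions after an earlier protocol PET.** With n patients and m scans each, n(m - 1) of nm sessions follow an earlier protocol PET.

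- Planned average (section 11: n = 20, m = 3): 20 × 2 = 40 of 60, or 67%.
- Maximum (section 7: m = 6): 20 × 5 = 100 of 120, or 83%.

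**3. Enrollment point #1.** Its first session is the staging scan, which gets no mrTRG, so its first mrTRG (restaging) already follows a protocol PET. If a fraction f of the 20 patients enters there and m = 3, there are 60 - 20f mrTRG reads, of which 40 follow a protocol PET. The documents do not give f.

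| f (assumed) | mrTRG reads | after a protocol PET | before any protocol PET |
|---|---|---|---|
| 0 | 60 | 40 (67%) | 20 |
| 0.5 | 50 | 40 (80%) | 10 |
| 1 | 40 | 40 (100%) | 0 |

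**4. Effect on the pooled rate.** Let p be the change rate in reads made before any protocol PET, r the ratio of the later rate to p, and w = 2/3 the share of later reads. Then pooled rate = p(1 - w) + p·r·w. Both p and r are assumptions.

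| r | p = 10% | p = 20% | p = 30% |
|---|---|---|---|
| 0.25 | 5.0% | 10.0% | 15.0% |
| 0.5 | 6.7% | 13.3% | 20.0% |
| 0.75 | 8.3% | 16.7% | 25.0% |
| 1 | 10.0% | 20.0% | 30.0% |
| 1.25 | 11.7% | 23.3% | 35.0% |
| 1.5 | 13.3% | 26.7% | 40.0% |

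For example, p = 20% and r = 0.5 gives 0.20 × 1/3 + 0.20 × 0.5 × 2/3 = 0.133. Values of r below 1 correspond to earlier PET findings being absorbed into the mrTRG. Values above 1 are possible too (see the objection).

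**5. Precision.** At an assumed 20% change rate, one scan per patient (4/20) has an exact 95% CI of 5.7-43.7%. Sixty scans treated as independent (12/60) give 10.8-32.3%. The second interval is too narrow if a patient's scans are positively correlated.

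**The case against.** **The direction is not established.** A reader might infer that pooling must pull the result toward no added value. The documents do not support that. Only patients judged cCR continue surveillance, and that judgment already takes the pmrTRG into account, so the earlier PET in a continuing patient is usually reassuring. A reader anchored on it might grade the MRI too favorably at a true recurrence and then change the grade when the new PET is opened, which means more changes. PET/MRIs are also roughly six months apart, so a recurrence that arose since the last one cannot already be reflected in its report. And the endpoint counts changes without specifying a direction, so fewer changes is not the same as less added value. This objection stands.

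**A different later rate need not mean contamination.** Restaging looks for residual disease, while later scans look for recurrence in patients selected as cCR. The rates may differ for that reason alone. This stands too, and it is a reason to show the two sets apart.

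**One reader for all sessions is an inference.** The sameness stated in 10.2 links the MRI and PET reads of one session. Nor do the documents say that earlier PET is consulted, only that it is available. Both stand, but the point does not depend on a single reader, because any later reader can open the chart.

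**Restricting the main analysis to first scans would undercut the objective.** For enrollment points #1 and #2 the first post-treatment scan is the restaging scan, so recurrence would be left to supportive data. It would also not remove prior PET for enrollment point #1. This stands against a first-scan-only analysis. It does not stand against reporting both sets.

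**Conclusion.** The point holds as a gap in the comparator and in the analysis set. After the first protocol PET, the plan does not assure that the mrTRG is an MRI-only read. That covers 40 of 60 sessions at the planned average, and a larger share of the mrTRG reads if patients enter at point #1. The pooled change rate may be biased. Fewer changes is the plausible direction if earlier PET findings carry over, but neither sign nor size can be derived from the documents. With p = 20% and r from 0.25 to 1.5, the pooled rate runs from 10.0% to 26.7%, on both sides of the assumed rate. An understatement of fixed size would follow only from assuming its direction.

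Separately, an exact binomial interval on pooled scans ignores clustering within patients.

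The consequence is limited. This is a descriptive secondary endpoint in a pilot, with no test or decision threshold attached, and the primary endpoint and sample size are unaffected. The change is worth making because it costs little.

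**What to change.** Change the analysis wording in sections 10.2 and 11:

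1. Report the mrTRG-to-pmrTRG change rate for each patient's first post-chemoradiation PET/MRI: one scan per patient, with an exact 95% CI.
2. Report later surveillance sessions separately, with an interval that accounts for clustering by patient.
3. Flag enrollment point #1 patients in the first set, since their first mrTRG follows a staging PET, or show that set by enrollment point.
4. Keep the all-scan summary as descriptive, so that detection of recurrence stays covered.

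The first set is free of earlier protocol PET only for enrollment points #2 and #3. Section 7 does not require a prior FDG-PET for these patients, but it does not exclude one either.

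No scan is added, and clinical reading and reporting stay as they are. The cost is a wider interval for the first-scan estimate, as in step 5 of the working, on at most 20 patients and fewer among those with no earlier protocol PET.

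### The secondary endpoint is counted over all scans, but a PET upgrade that leads to surgery ends the patient's series, so a pooled rate does not show in how many patients PET added detection

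*Combined protocol and SAP*

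**What the plan says.** Section 4.2 gives the secondary objective: "To estimate the added value of PET/MRI relative to MRI only for detecting residual or recurrent rectal cancer". Section 10.2 makes the endpoint the difference between the MRI-only tumor regression grade (mrTRG) and the grade after PET is added (pmrTRG), recorded at each scan. It then states that "the secondary endpoint will consider all scans that each patient undergoes, rather than just the first scan". (That sentence attributes a first-scan rule to 10.1, although 10.1 includes all available scans. This is a separate matter.)

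The grade is also used in care. "The patient’s multidisciplinary care team will consider the pmrTRG in conjunction with results of other available data", such as endoscopy and digital examination, when it decides on cCR. Patients without cCR are evaluated for surgery. By contrast, "subjects deemed to have a cCR will continue on the NOM surveillance protocol, with repeat PET/MRIs at regular intervals", and those scans are analysed in the same way.

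Section 7 lists six sessions per enrollment point, on the assumption that no indication for surgery arises. The calendar in Section 12 says surveillance scans are omitted only when surgery is actually performed for suspected recurrence.

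Section 11 says the secondary endpoint "will also be analyzed with descriptive statistics, including exact 95% confidence intervals". It names no denominator for this endpoint, gives no per-patient summary and does not separate changes by direction. Its figures of 20 patients, 3 scans each and about 60 scans are stated for feasibility.

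**The concern.** The number of scans a patient contributes depends partly on the result being counted. Suppose PET moves a patient from complete response on MRI to residual or recurrent disease, and surgery follows. That patient adds one changed scan and then leaves; any earlier unchanged scans still count. Now suppose MRI suggests residual disease, PET clears it, and the team calls cCR each time. That patient can add a change at every session: up to six for enrollment points #2 and #3, and five for #1, whose first scan precedes treatment and carries no mrTRG.

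A proportion over all scans therefore gives little weight to the event the objective names, and it mixes that event with changes in the opposite direction. The overview says the data will guide the design of later PET/MRI trials. A designer who reads the pooled figure as the frequency of added detection would be misled about both its size and its direction.

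**Working it through.** **1. The plan's own figures.** Section 11 gives exact intervals only for the primary endpoint. Clopper-Pearson limits, treating scans as independent, are 68.3-98.8% for 18/20, which matches the plan. For 50/60 they are 71.5-91.7%, against the printed 72-92%. No expected change rate is given for the secondary endpoint, so every rate below is an assumption.

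**2. Counting asymmetry.** Inputs: 20 patients and 60 scans (Section 11). Assumed: 2 patients upgraded at their first post-treatment scan who then exit, 2 downgraded at every scan who stay, and 16 unchanged. Per patient, each direction is 2/20 = 10%.

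- Scans per staying patient: (60 - 2)/18 = 3.22.
- Pooled upgrades: 2/60 = 3.3%.
- Pooled downgrades: 2 x 3.22/60 = 6.44/60 = 10.7%.

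At the schedule's maximum, with all patients at enrollment points #2 or #3, there are 2 + 18 x 6 = 110 scans. Upgrades are 2/110 = 1.8% and downgrades 12/110 = 10.9%.

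**3. Sensitivity to exit (60 scans, assuming an upgrade would persist at later scans).**

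| Upgraded patients who exit | Pooled upgrades | Pooled downgrades |
|---|---|---|
| 2 of 2 | 2/60 = 3.3% | 6.44/60 = 10.7% |
| 1 of 2 | (1 + 59/19)/60 = 4.11/60 = 6.8% | 2 x (59/19)/60 = 6.21/60 = 10.4% |
| 0 of 2 | 6/60 = 10% | 6/60 = 10% |

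The gap shrinks as fewer upgrades lead to surgery, and vanishes when none do.

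**4. Is the pooled figure wrong as a per-scan rate?** Let a patient have upgrade risk p at each of up to m sessions, with scanning ending at the first upgrade. Expected upgrades are 1 - (1 - p)^m, and expected scans are [1 - (1 - p)^m]/p.

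- *Equal risk.* The ratio is p whatever m is. With p = 0.10 the pooled rate is 10%, a valid per-scan rate. The share of patients ever upgraded is different: 1 - 0.9^3 = 27% at 3 sessions and 1 - 0.9^6 = 47% at 6.
- *Unequal risk.* Assume p = 0.50 in one sixth of patients and 0.02 in the rest. The average per-scan risk is 0.50/6 + 0.02 x 5/6 = 10%, which is also the expected first-scan rate.
  - m = 3: upgrades 0.875/6 + 0.0588 x 5/6 = 0.195; scans 1.75/6 + 2.940 x 5/6 = 2.742; pooled rate 7.1%.
  - m = 6: upgrades 0.984/6 + 0.1142 x 5/6 = 0.259; scans 1.969/6 + 5.708 x 5/6 = 5.085; pooled rate 5.1%.
  - m = 6 with half of upgrades ending the series: replace p by p/2 in the scan formula and multiply scans by p for upgrades. Scans are 3.288/6 + 5.852 x 5/6 = 5.425; upgrades 1.644/6 + 0.1170 x 5/6 = 0.372; pooled rate 6.8%.
  - With no exit the pooled rate returns to 10%.

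**5. Precision.** Exact 95% limits are 1.2-31.7% for 2/20 and 0.4-11.5% for 2/60.

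**The case against.** The strongest reply is that pooling is inferred. Considering all scans could also mean a per-patient summary of any change, and Section 9 has the monitoring report list how many participants met each objective. But Section 9 concerns monitoring, and nothing in 10.2 or 11 sets a per-patient analysis. All scans together with exact intervals points to pooling, and if that was not intended, the wording still needs to say so.

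Second, a per-scan change rate is a legitimate target for a test that informs a decision at each session, and under equal risk exit does not distort it. That stands. The problem is then that it answers a different question from the number of patients with added detection.

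Third, exit is not certain. An upgrade is weighed with other findings, loss of cCR leads only to evaluation for surgery, and Section 12 omits scans only after surgery. Surgery prompted by MRI findings shortens series too. The frequency of a lasting downgrade has no support in the documents. These points limit the size, and the illustration is labelled accordingly.

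Fourth, a proportion of patients ever changed also grows with follow-up, as the 27% and 47% above show. It should not stand alone.

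A reader might go further and apply the interim results in Section 3.1 (1 of 9 without cCR, then 1 of 8 losing it), inferring that a true 2/9 = 22% would be reported several-fold too low. The documents do not support this. Going from 22.2% of patients to 22.2/3 = 7.4% of scans is a change of unit with no exit effect. At six sessions without exit, one change each gives 2/54 = 3.7%, so exit alone does not produce the low figure. Those failures were also judged by MRI, digital examination and endoscopy, not by PET. No section sizes a future trial on this rate.

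**Conclusion.** The point holds in a limited form. As written, the plan leads to a pooled proportion whose denominator depends on the result and which mixes two opposite kinds of change. It does not estimate in how many patients PET added residual or recurrent disease. It also understates the average per-scan upgrade rate when risk differs between patients and upgrades end scanning: 10% becomes 7.1% at 3 sessions and 5.1% at 6 under the assumed split. Equal patient-level rates of 10% can appear as 3.3% against 10.7% at about 60 scans. That example assumes that both upgraded patients exit and both downgrades persist.

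A reader might infer that the pooled rate is biased in every case. It is not, since it remains valid per scan when risk is equal. The endpoint is secondary and descriptive, with no decision threshold, and the grades are recorded at each scan, so better summaries remain recoverable. The change is still worth making before analysis, because the data are meant to inform later trials.

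**What to change.** In 10.2 and Section 11:

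- Define an upgrade (complete on MRI, residual or recurrent on PET/MRI) and a downgrade (the reverse), and report them separately.
- Give each as a per-patient proportion with an exact 95% interval, over patients with at least one post-treatment PET/MRI. Report it at the first post-treatment PET/MRI and as ever changed, with the number of scans per patient stated alongside.
- Add the change rate by session among patients still being scanned at that session.
- Keep the pooled all-scan rate as a supplementary description, with its denominator named.

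Separately, Sections 7, 10.2 and 12 tie the end of scanning to a surgical indication, to loss of cCR and to surgery performed, respectively. These passages must be reconciled so that the denominators are defined.

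The cost is wording and a little more tabulation, with no new patients, scans or reads. The drawback is a wider interval, as in step 5, because the denominator is about 20 patients and not about 60 scans.
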